9. PHARMACODYNAMIC ANALYSIS

Analysis of pharmacodynamic endpoints will include summaries of liver biochemical parameters (ALT, AST, GGT, total bilirubin, bilirubin, albumin, and alkaline phosphatase), serum lipids (serum total cholesterol, LDL, HDL, and triglycerides), serum ferritin, hsCRP, and platelets which will be tabulated overall and by dosing cohort. Observed values, change from baseline and percent change from baseline at each time of assessment will be summarized, and will include 95% confidence intervals. P-values may be calculated if there are a minimum of 6 subjects across all cohorts available for analysis at a particular timepoint; if presented, these will be computed using Wilcoxon-sign-rank statistics on change from baseline.

Serum lipids, serum ferritin, and hsCRP will be presented by-subject and tabulated in both SI and Conventional units; all other laboratory data will be presented as SI units only. In addition, the proportion of subjects with abnormal transaminases, serum lipids, serum ferritin and hsCRP will be displayed by cohort and overall.

Shift tables comparing the percentages of subjects (pooled across dosing cohorts) with normal/abnormal values for each pharmacodynamic parameter at each time of assessment relative to the CL04 baseline will be presented.

Graphical displays may be created to illustrate the time course of these lab parameters, including spaghetti plots and mean plots. Graphical displays may also be used to investigate differences in lipid results from assessments taken one week after infusion versus those taken 2 weeks after infusion.

Change from baseline analyses for PD endpoints will be performed using CL01 and CL04 baselines.

10. PATIENT HEALTH-RELATED QUALITY OF LIFE (HRQOL) OUTCOMES ANALYSES

Observed scores and changes from the CL01 and CL04 baseline will be summarized for HRQOL measures including the 36-item Short Form Health Survey (SF-36), Functional Assessment of Chronic Illness Therapy (FACIT-Fatigue) scale, and Chronic Liver Disease Questionnaire (CLDQ). All score data will be presented by study visit in data listings.

For SF-36 scores, scores for the 8 subscales (Physical Functioning, Role Physical, Bodily Pain, General Health, Vitality, Social Functioning, Role Emotional and Mental Health) as well as the Physical Component Summary (PCS) and Mental Component Summary (MCS) will be derived and summarized. Both transformed scores (0 – 100 scoring) and norm-based scores will be presented. The FACIT-Fatigue Total Score, Total CLDQ score, and the 6 subscales of the CLDQ (Abdominal Symptoms, Fatigue, Systemic Symptoms, Activity, Emotional Functions and Worry) will also be listed and tabulated. Observed measurements and changes and/or percent changes from baseline to study time points will be summarized overall and by dosing cohort including 95% confidence intervals.

These analyses will be based on the FAS.

11. SAFETY AND TOLERABILITY ANALYSIS

The analysis of safety and tolerability will include the following data:

- SBC-102 exposure.
- Adverse events. o AEs (i.e., treatment-emergent AEs), including related AEs and SAEs. o AEs causing study discontinuation.

 \circ Infusion related reactions.

- Clinical laboratory investigations.
- Vital signs (body temperature, pulse rate, respiratory rate, blood pressure).
- Physical exam.
- 12-Lead ECG.
- Concomitant medications and therapies.
- Antidrug antibody formation.

These analyses will be based on the Safety Analysis Set.

11.1 SBC-102 Exposure

Exposure to study drug (SBC-102) will be summarized by dose. The total number of infusions attempted, the number of infusions completed both without and with a rate change or infusion interruption and the number of infusions where the entire infusion volume was not administered will be presented.

A data listing will be presented, sorted by subject within initial dose of SBC-102, providing the dates, total planned and actual volumes of drug infused, infusion rate and duration of the each infusion along with any modification to the infusion.

11.2 Adverse Events

An AE is any untoward medical occurrence in a subject, which does not necessarily have to have a causal relationship with the administration of a pharmaceutical product. An AE can therefore be any unfavorable and unintended sign, symptom or disease temporally associated with the use of the medicinal product, whether or not considered related to the medicinal product. Pre-existing conditions that worsen in severity during the course of the study are to be reported as AEs.

Severity of AEs will be graded on a 5-point scale (mild, moderate, severe, life-threatening and death) according to National Cancer Institute (NCI) Common Terminology Criteria for Adverse Events (CTCAE), version 4.03. All AEs will be coded using the Medical Dictionary for Regulatory Activities (MedDRA[®]), version 13.1 or higher.

In AEsummaries, subjects will only count in one column.

For counting events, if a subject experiences the same AE multiple times, each occurrence of this event will be counted toward the frequency of events; but for counting subjects, each subject will be counted only once within each PT and each SOC. If a subject experiences more than one AE within a PT or SOC, only the AE with the strongest relationship or the greatest severity, as appropriate, will be included in the summaries of relationship and severity, respectively.

A data listing of all AEs reported in the study will be presented.

Additionally a data listing of deaths and AEs leading to study discontinuation will be provided.

11.2.1 Serious Adverse Events

Summaries of the numbers of SAEs and incidence rates (frequencies and percentages of subjects), by PT within SOC, overall and by dosing cohort, will be prepared for the Safety Analysis Set.

A data listing of SAEs will be provided.

11.2.2 InfusionAssociated Reactions

Infusion reactions will be considered Medical Events of Interest (MEOI). An AE will be considered an IAR if the Investigator checks "Yes" to the question "Is AE an IAR?" on the AE CRF. In addition, for the purpose of this study, an AE (diagnosis and/or symptom) that occurs from the start of the infusion, up to 4 hours after the infusion and is assessed by the Investigator as at least possibly related to SBC-102 will be considered an IAR. Note that several AEs may be associated with one IAR observed with SBC-102 administration; each AE is captured as a separate event. The number and percentage of subjects who experience any IAR (any subject who experiences an IAR is only counted once regardless of the number of associated events) and the number of IARs reported over the course of the study (i.e., subjects may be counted more than once if IARs occur on more than one dosing day) will be summarized.

Summaries of AEs that comprise an IAR will be presented in a similar manner to AEs in Section 11.2.

A data listing of all AEs reported as IARs during the study will be presented.

IMP infusions in which the rate was slowed or which were discontinued due to IAR will also be detailed in data listings along with an indication of whether the subject developed one or more antidrug antibodies during the course of the study.

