8.6 Study Treatment Usage and Compliance

Number of weeks in the study and number of study infusions received by subjects will be summarized overall, by dosing regimen, by dose across all frequencies and by frequency (qw or qow). Descriptive summaries of rate of infusion, volume, and number (percent) of subjects who receive all study infusions 'per protocol' (i.e., subjects without missed infusions or infusion interruptions or rate changes) will also be provided.

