8.7 Safety Analysis

Safety will be analyzed in Safety Analysis Set. As appropriate, the effect of dosing regimen and/or treatment duration on safety endpoints will also be explored.

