5. STATISTICAL ANALYSIS

5.1 General Statistical Methodology

All data will be provided in listings sorted by cohort and subject study number, and, if applicable, date of assessment. Dates will be provided in the ISO8601 yyyy-mm-dd format (eg, 2013-01-01). Where a time component is included (24 hour clock with hour and minute) the format will be yyyy-mm-dd:hh:mm (eg, 2012-01-01:16:32). Included in all listings will be the dosing cohort for each subject. Select listings will also include the dosing regimen that each subject was on at the onset of the event.

Tabulations will be prepared using the following descriptive statistics:

- Continuous, quantitative variable summaries will include the number of subjects with non-missing values (n), mean, standard deviation (SD), minimum, median, and maximum. In addition, the percent coefficient of variation (CV%) will be provided for PK parameters.
- Categorical, qualitative variable summaries will include the frequency and percentage of subjects who are in the particular category. In general, the denominator for the percentage calculation will be based upon the total number of subjects in the analysis set for the cohort. Shift tables comparing data observed at baseline to that observed after the initiation of dosing will be prepared as noted for specific endpoints.

95% two-sided confidence intervals (CI) may be calculated around the estimates based on the exact binomial distribution for categorical endpoints and the t-distribution for continuous endpoints. Confidence intervals will be based on a 2-sided alpha of 0.05 and are intended to guide clinical judgment and interpretation of the data. Effect of anti-drug antibodies may be examined for efficacy, safety, and PK endpoints. Additional exploratory analyses may be conducted in other subgroups of interest.

Baseline values are defined as the last measurement prior to the first infusion of SBC-102 in study LAL-CL04.

For select continuous efficacy, safety, and HRQOL endpoints that are computed as changes from baseline, change from the CL04 Baseline will be presented. All tabulations will present data overall and by dosing cohort.

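### Infusion-associated reactions get no rate per infusion, and the infusion counts are grouped differently from the reactions, so no valid comparison by regimen is prespecified

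*SAP*

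**What the plan says.** **IAR summaries.** SAP 11.2.2 plans "The number and percentage of subjects who experience any IAR" and "the number of IARs reported over the course of the study". The second allows a subject to count again when reactions fall on different dosing days. The general rule in SAP 5.1 for percentages is that "the denominator for the percentage calculation will be based upon the total number of subjects in the analysis set for the cohort". No rate per infusion or per subject-year appears in the SAP.

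**Columns.** SAP 4.4 defines a cohort by the subject's every-other-week dose, and SAP 11.2 lets a subject count in only one column of an AE summary. SAP 11.2.2 presents the AEs that make up an IAR in the same manner. The regimen at event onset is promised only for selected listings (SAP 5.1).

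**Exposure.** SAP 11.1 states: "Exposure to study drug (SBC-102) will be summarized by dose". It keeps "The total number of infusions attempted, the number of infusions completed both without and with a rate change or infusion interruption", plus incomplete infusions. A by-subject listing gives dates, volumes and "infusion rate and duration of the each infusion along with any modification to the infusion". That duration is the length of each infusion, not time on treatment.

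**Protocol.** Section 8.6 says: "Number of weeks in the study and number of study infusions received by subjects will be summarized overall, by dosing regimen", and also by dose across frequencies and by frequency. Section 8.7 says that, as appropriate, "the effect of dosing regimen and/or treatment duration on safety endpoints will also be explored". Section 8.7.1 adds, again as appropriate, summaries of IAR frequency and severity over time.

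**Declared changes.** SAP Section 14 declares the move to cohort tabulation. It does not mention weeks in study, the frequency split of exposure, or the IAR-over-time summaries.

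**The concern.** An IAR can occur only if an infusion is given, so the natural unit of risk is the infusion. Subjects in this study may receive very different numbers of infusions: follow-up can run for years, some may leave early, and Protocol 3.1 allows a change from 3 mg/kg every other week to 3 mg/kg weekly after Week 12. A percentage of subjects or a raw count mixes risk per infusion with the number of infusions. A cohort in which several subjects moved to weekly dosing, or stayed longer, will tend to show more IARs at the same risk per infusion.

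The planned exposure table does not supply the right denominator. It is cut by dose while the reactions are cut by every-other-week cohort. For example, an IAR during a 0.35 mg/kg starting infusion is credited to the subject's every-other-week cohort, but that infusion is counted under 0.35 mg/kg. A reaction on 3 mg/kg weekly has no column of its own in either table. Dividing one table by the other, group by group, would give a wrong rate.

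Long-term safety is the primary objective, and IARs are AEs of special interest and one of the primary safety endpoints. The study's output is descriptive, so the choice of description matters.

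**Working it through.** The documents state no IAR rate and no power or event calculation, so there is no plan figure to reproduce. The check counts scheduled infusions and shows how far the planned summaries move when risk per infusion is held equal.

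**Step 1. Infusions every other week.** Protocol Appendix A schedules infusions at Weeks 1 to 4, then every 2 weeks from Week 6.
- To Week 260: 4 + [(260 − 6)/2 + 1] = 4 + 128 = 132. Check against the schedule's blocks: 14 (to Week 24) + 14 (Weeks 26–52) + 4 × 26 = 132.
- To Week 156, the 3 years stated in SAP 3.1: 14 + 14 + 2 × 26 = 80.
- Whether the Week 260/end-of-study column includes an infusion is ambiguous; this changes a count by at most 1.

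**Step 2. Infusions after a switch to weekly dosing.** Infusions up to switch week s, plus one per week afterwards (end − s).

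| Switch after | To Week 260 | Ratio to 132 | To Week 156 | Ratio to 80 |
|---|---|---|---|---|
| Week 12 | 8 + 248 = 256 | 1.94 | 8 + 144 = 152 | 1.90 |
| Week 52 | 28 + 208 = 236 | 1.79 | 28 + 104 = 132 | 1.65 |
| Week 104 | 54 + 156 = 210 | 1.59 | 54 + 52 = 106 | 1.325 |

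If the first weekly infusion is at Week 14 rather than Week 13, the top row becomes 255 (1.93) and 151 (1.89).

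**Step 3. Effect on the planned summaries.** Assume a risk p per infusion, equal across regimens and independent between infusions. Then P(any IAR) = 1 − (1 − p)^n and expected IARs = np. For n = 132 against n = 256:

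| Assumed p | P(any IAR) | Expected IARs | Per 100 infusions |
|---|---|---|---|
| 0.1% | 12% vs 23% | 0.13 vs 0.26 | 0.1 in both |
| 0.5% | 48% vs 72% | 0.66 vs 1.28 | 0.5 in both |
| 1% | 73% vs 92% | 1.32 vs 2.56 | 1.0 in both |
| 2% | 93% vs 99% | 2.64 vs 5.12 | 2.0 in both |

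**Step 4. Where the difference sits.** Both cohorts are defined by an every-other-week dose, so the difference arises inside a cohort. In an assumed cohort of 6 followed to Week 260, one subject switching after Week 12 raises mean infusions from 132 to (256 + 5 × 132)/6 = 152.7 (ratio 1.16). Three switching gives (3 × 256 + 3 × 132)/6 = 194 (1.47).

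**Step 5. Unequal follow-up.** A subject on every-other-week dosing who leaves at Week 52 has 28 infusions against 132 at Week 260, a ratio of 132/28 = 4.7. At p = 0.5%, P(any IAR) is 1 − 0.995^28 = 13% against 48%. Follow-up can therefore matter more than frequency.

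**The case against.** The strongest reply is that little is lost. SAP 11.1 still reports infusions attempted, and SAP 11.2.2 counts IARs by dosing day, so an overall ratio follows from two planned outputs. With at most 9 subjects, every infusion and every IAR is listed, and selected listings give the regimen at onset. SAP Section 12 plans no between-cohort tests, so no error rate is affected. All of this stands. A reader might infer that regimens cannot be compared at all; the listings show that they can. What is missing is a prespecified comparison.

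A reader might also infer that time in study has been removed without notice. SAP 4.3 says that planned analyses in both the protocol and the SAP will be performed, with changes listed in Section 14. On that reading the Protocol 8.6 summaries remain in force and SAP 11.1 is an incomplete restatement. Section 14 also openly declares the move from regimen to cohort. Removal is therefore not established; the SAP leaves it unclear. The protocol's analyses of safety by regimen or duration, and of IARs over time, are in any case qualified as appropriate.

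Three further readings go too far. IARs are one of several primary safety endpoints, and neither document ranks them first. The near two-fold gap does not lie between SAP columns, since there is no weekly column. And that gap is close to a worst case: it needs a switch at the first opportunity, Protocol 6.1.1 requires an inadequate response before escalation, and no switching frequency is given. Nor need early leavers always look safer, because a subject who leaves after an IAR is still counted.

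None of this supplies a matched numerator and denominator by regimen.

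**Conclusion.** The point holds as a descriptive weakness that is cheap to repair. The SAP prespecifies no IAR rate per infusion, and its infusion counts and IAR counts are grouped in ways that do not match, so no valid regimen-specific comparison is planned. It also does not carry forward the weeks in study or frequency split of Protocol 8.6, nor the IAR-over-time summary of Protocol 8.7.1, and Section 14 declares only the move to cohorts.

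The size depends on when a subject switches and how long they are followed. The infusion ratio runs from about 1.9 for the earliest switch down to 1.59 (Week 104 switch, 5 years) or about 1.3 (Week 104 switch, 3 years), and it reaches 4.7 for Week 52 against Week 260 follow-up on every-other-week dosing. The 48% against 72% figure rests on an assumed 0.5% risk per infusion that is constant, independent and equal across regimens. Protocol 1.5.2 notes that antibodies to approved enzyme replacement therapies may raise the risk of infusion reactions, so a constant risk is an illustration and not a forecast. The consequence is for interpretation of the safety description, not for any test.

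**What to change.** - **SAP 11.2.2:** add IARs, counted by dosing day, per 100 infusions. Assign both events and infusions to the regimen (dose and frequency) in force at that infusion. SAP 8.1.4 already follows this principle for PK concentrations, using the dose at the infusion instead of the cohort. Show the rate overall and by regimen, with an overall-only summary by study year, and exempt this table from the one-column rule. Adding a rate inside the existing cohort columns would not be enough.
- **SAP 11.1:** restore weeks in study and number of infusions overall, by regimen, by dose and by frequency, or list their removal in Section 14. Do the same for the IAR-over-time summary, which the study-year table would largely meet.
- **Duration:** reconcile the 3 years in SAP 3.1 with the 5 years in Protocol 3.2.3, since the exposure summaries depend on it.

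The cost is one more descriptive table and some programming. Infusion dates, volumes and actual dose amounts are already recorded, so no new data are needed. With at most 9 subjects the regimen cells will be sparse, so numerators and denominators should be printed beside each rate. Subject-year rates for all AEs and SAEs would be a reasonable addition but are optional.

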11.3 Clinical Laboratory Evaluations

Observed measurements and changes/percent changes from the CL01 and CL04 baseline to study time points in clinical chemistry, hematology, and urinalysis will be summarized by dosing cohort and overall. All laboratory values will be classified as normal, above normal, or below normal based on normal ranges provided by the laboratory. All laboratory values will be presented in data listings. Results will be flagged to indicate if they were abnormal (high, low) and/or clinically significant. Frequencies of abnormal values relative to the laboratory normal range will also be summarized via shift tables.

Information relating to development of anti-drug antibodies will be provided in listings.

Spaghetti plots for actual, change from baseline, and percent change from baseline will be created for the following parameters: ALT, AST, GGT, total bilirubin, albumin, alkaline phosphatase, total cholesterol, LDL-C, HDL-C, triglycerides, hemoglobin, platelets, PT, PTT, and serum ferritin. Plots will include a line for each subject with line color to indicate cohort plus a black line for the overall mean.

Plots of mean absolute change and mean percent change over time with standard deviations as error bars may be prepared for the following:

- Liver biochemical parameters: ALT/AST, GGT, bilirubin, albumin, alkaline phosphatase
- Lipids: total cholesterol, LDL, HDL, triglycerides
- Other: Hemoglobin, platelets, PT/PTT, serum ferritin

Change from baseline analyses will be performed using CL01 and CL04 baselines.

11.4 Vital Signs

Observed values and change from pre-dose will be presented for the following vital sign parameters, where applicable:

- Body temperature.
- Pulse rate.
- Blood pressure.

• Respiratory rate.

A listing of the vital signs measurements will be also provided.

11.5 Electrocardiograms

Change from CL01 and CL04 baseline in the ECG parameters will be provided, where applicable. Categorical summaries (e.g. normal, abnormal, abnormal clinically significant) will also be presented. A listing of ECG results will be provided.

11.6 Physical Examination

Summaries of physical examination findings by body system as well as summaries of clinical significance of findings, size and characteristics of the liver, spleen and lymph nodes, and palpability of the tibialis and pedis pulse will be summarized at baseline and post baseline.

A summary of findings including liver size, spleen size, lymphadenopathy and arterial disease at Screening and follow-up will be presented.

11.7 Concomitant Medications and Therapies

Concomitant medications include prescription and over-the-counter medications, herbal medications, prophylactic and therapeutic vaccines, vitamins, and dietary supplements. Concomitant treatments include diagnostic, palliative, or interventional procedures. The name of the medication or therapy, reason for use, start date, stop date, dose and route of administration (if applicable), and frequency of administration will be reported as in the eCRF.

Prior medications and concomitant medication/treatment data will be coded using the WHODRUG dictionary (March 2011 edition). All data will be listed, and the number and percentage of subjects receiving each prior and concomitant medication/treatment by ATC class and/or preferred term as appropriate will be tabulated.

All prior medications and concomitant medications and treatments (pharmacological and nonpharmacological) received by the subject from the last assessment in LAL-CL01 until completion of the follow-up visit approximately 30 days after the last does of SBC-102 will be provided in a data listing. The data listing will include start and end dates (or indication of ongoing), dose, unit, frequency, route, and an indication of whether the medication usage is prior, concomitant or both.

11.8 Antidrug Antibody Titer

The proportion of subjects with measurable antibodies to SBC-102 will be displayed overall and by cohort. A data listing will be provided.

12. TREATMENT GROUP ANALYSIS

This is a Phase 2 drug safety and PK/PD study. No formal statistical hypothesis testing is planned to compare between cohort (treatment group) effects.

